## 1.B RATIONALE

The goal of the study is to evaluate a Home-Based Disease Management program specifically adapted for patients with GOLD III/IV COPD. Acute episodes requiring hospitalisation are more frequent in these patients with severely compromised lung function. Additionally, they are major contributors to health status decline and health costs. Therefore, the study primary objective is to show a significant reduction in the number of hospital days during the 12-month study follow-up in patients receiving the study program as compared to patients receiving usual care.

Key interventions of the study program combine four components of chronic care: *i) patient education, ii) patient motivation (to promote self-efficacy and self-management), iii) closer patient follow-up to allow early detection of significant clinical worsening, and iv) coordination of health care to reduce time to treatment.*

During the study, **patients of the Intervention group will receive an educational program provided by community-based health professionals** individually at home, in group sessions, and by telephone. The study educational program was adapted from the original 'Living Well With COPD' program, initiated, evaluated and implemented in Canada by the Montreal Chest Institute of the McGill University Health Centre since 1998. This program has been shown to have a sustained positive impact on patient's health, on health-related quality of life, and on the use of acute hospital care, resulting in significant cost of care savings. The program contains disease knowledge education because it is essential for patients with COPD to understand their disease, risk factors for its progression, and objectives of their medication in order to promote compliance to therapeutics, including oxygen therapy, and to encourage "healthy behaviours" such as smoking cessation and regular physical activity. The program also contains a patient-tailored 'action plan' that includes teaching of techniques to self-perform home respiratory assessments, and specifying the steps to follow in particular situations, such as acute worsening of respiratory symptoms, so as to reinforce the patient's role in achieving better disease control.

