### 4.A STUDY DESIGN

This is an international, multicentre, open, randomised, prospective, controlled, parallel-group Phase IV study. It will be conducted in four (4) countries (France, Germany, Italy and Spain) and approximately forty-five (45) investigational centres.

Included patients will be randomly assigned by centre, smoking status and need for respiratory assistance (*i.e.*, *home oxygen therapy or Non-Invasive Ventilation*) for chronic respiratory failure at Selection to one of the two (2) study groups:

- Either Home-Based COPD Management group (*Intervention group*),
- Or the Usual COPD Education and Patient Follow-Up group (*Control group*).

**Figure 1:** Schematic Study Design

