#### **4.B.2 Method of assigning patients to study groups**

According to their smoking status, their need for respiratory assistance (*i.e., home oxygen therapy or Non-Invasive Ventilation*) for chronic respiratory failure at Selection and their investigational centre, included patients will be randomly assigned to either the Intervention group or the Control group, according to a computer generated randomisation list pre-specified prior to the study start. The randomly allocated study group to a given included patient and the corresponding 4-digit randomisation number will be attributed in sequential numerical order by the study dedicated telephone Interactive Voice Response System (IVRS). This randomisation number will be used throughout the study as the identification number for all randomised patients.

The randomly allocated study group and the corresponding 4-digit randomisation number will be notified to the investigator through the IVRS and they will be confirmed automatically *via* an e-mail and/or fax sent to the investigator. The investigator will print the randomisation confirmation e-mail/fax and file it in the investigator binder.

Neither the patient nor the study personnel of the investigational centre will be blinded as to the study group allocated, after randomisation.

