**Respiration rate evaluated by the *NOWOX* device:** the average daily respiration rate and the average daily peak respiration rate will be calculated separately over the same periods and in the same way as the average daily use of oxygen therapy. Both estimations of the respiration rate will then be tabulated, analysed and represented graphically in exactly the same way as the average daily use of oxygen therapy previously described (*except its last part related to the relative and absolute individual differences between the *NOWOX* estimations and the actual prescriptions of oxygen therapy*).

**Changes in smoking status:** from Visit 1 onwards, the number and percentage of patients who are current smokers and the number and percentage of patients who are ex-smokers will be tabulated by study group and visit. The corresponding histogram will also be produced.

Moreover, from Visit 1 onwards, a shift table will be provided by study group and visit to depict the number and percentage of patients with the four (4) possible categories of smoking status evolution since their Selection (*Visit 0*):

- number and percentage of patients ex-smokers at Visit 0 and ex-smokers at the post-Run-In tabulated visit,
- number and percentage of patients current smokers at Visit 0 and current smokers at the post-Run-In tabulated visit,
- number and percentage of patients ex-smokers at Visit 0 and current smokers at the post-Run-In tabulated visit,
- number and percentage of patients current smokers at Visit 0 and ex-smokers at the post-Run-In tabulated visit.

At each visit separately, the smoking status evolution since Visit 0 will be compared between both study groups using either the Pearson's Chi-Square test or the Fisher's exact test depending on their distribution.

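### The between-group test of smoking status change runs over categories that contain Visit 0 status, so it is somewhat conservative and weaker for a cessation effect than a comparison within Visit 0 status

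*Protocol*

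**What the plan says.** Protocol section 7.B.3.5, under changes in smoking status, plans a shift table by study group and visit, "with the four (4) possible categories of smoking status evolution since their Selection". The four are ex-smoker at both times, current smoker at both times, ex-smoker turned current, and current smoker turned ex. The closing sentence of that part gives the test, to be run visit by visit: "the smoking status evolution since Visit 0 will be compared between both study groups using either the Pearson's Chi-Square test" or Fisher's exact test, depending on the distribution. No comparison restricted to Visit 0 smokers, and none stratified by Visit 0 status, is written.

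Section 4.B.2 makes smoking status a randomisation factor: "According to their smoking status, their need for respiratory assistance" and their centre, patients are allocated "according to a computer generated randomisation list pre-specified prior to the study start". Section 4.A plans "approximately forty-five (45) investigational centres". Block size is not given.

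Section 7.B makes every result other than the primary analysis exploratory and descriptive, tested two-sided at 5.0% without multiplicity adjustment. Change in smoking status is a listed secondary criterion. Section 1.B names smoking cessation among the behaviours the programme should encourage, and Table 1 places it in the fourth individual session.

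**The concern.** The tested variable mixes three quantities: the share of smokers at Visit 0, quitting among Visit 0 smokers, and relapse among Visit 0 ex-smokers. Only the last two can respond to treatment. The first is fixed before treatment, and stratification pushes its between-group difference towards zero, yet it still adds a degree of freedom to the reference distribution. The test therefore rejects less often than its nominal level when nothing is going on, and it dilutes a cessation effect when there is one.

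It also departs from the protocol's own practice. SGRQ-C, 15D, HADS, spirometry, walking distance, echocardiography and BODE are all analysed with the Run-In value as covariate. For smoking status the baseline value is part of the outcome instead.

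At stake is a missed or blurred exploratory signal on a behaviour the programme sets out to change.

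**Working it through.** **Inputs from the protocol.** 306 randomised, 153 per group; two-sided 5%; about 45 centres x 2 smoking classes x 2 respiratory-assistance classes = 180 strata, so 306/180 = 1.7 patients per stratum on average. The protocol states no size or power for this test, so there is no figure of its own to reproduce.

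**Assumed, because the protocol gives no value.** Share of current smokers at Visit 0, quit rates, relapse rates and block size.

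**1. Size under exact balance.** If the groups hold equal numbers of Visit 0 smokers and ex-smokers, the 2x4 Pearson statistic is exactly the sum of the 2x2 statistic for quitting and the 2x2 statistic for relapse. Under the null it follows approximately chi-square on 2 df, but it is referred to the 3 df cut-off of 7.815. Size = P(chi-square on 2 df > 7.815) = exp(-7.815/2) = 0.020.

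**2. Power, one worked case.** 30% smokers gives about 46 per group. Quitting is 10% against 25%, with relapse equal in both groups. Noncentrality = (46/2) x 0.15² / (0.175 x 0.825) = 3.58.
- Quit test, 1 df, cut-off 3.841: power 47%.
- Four-category test without stratification, 3 df, cut-off 7.815: power 32%.
- Four-category test with exact balance, 2 df law, cut-off 7.815: power 25%.

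Of the 22-point loss, 15 points come from using a 3 df test for one contrast and 7 from the balance.

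**3. Balance is only partial.** With so few patients per stratum many blocks stay incomplete, so the size was simulated over 20-50% smokers, quit rates of 10-20% and relapse of 2-10%, with N = 306:
- exact balance: 1.1-2.1%
- blocks of 2: 1.4-2.7%
- blocks of 4: 1.7-3.3%
- blocks of 6: 2.3-3.7%
- no stratification: 3.6-5.1%

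**4. Power by simulation.** N = 306, 4,000 trials per row, Monte Carlo standard error at most 0.8 points. CMH is the Cochran-Mantel-Haenszel test of current smoking stratified by Visit 0 status.

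| Smokers | Quit, control v intervention | Relapse, control v intervention | Allocation | Four-category | Quit test | CMH |
|---|---|---|---|---|---|---|
| 30% | 10 v 25% | 5 v 5% | exact balance | 24.3% | 50.4% | 30.0% |
| 30% | 10 v 25% | 5 v 5% | blocks of 4 | 28.3% | 48.8% | 30.1% |
| 30% | 10 v 25% | 5 v 5% | no stratification | 32.6% | 47.7% | 30.1% |
| 30% | 10 v 30% | 5 v 5% | blocks of 4 | 47.1% | 68.8% | 44.5% |
| 40% | 10 v 30% | 5 v 5% | blocks of 4 | 62.0% | 80.7% | 64.5% |
| 30% | 15 v 30% | 10 v 3% | blocks of 4 | 57.6% | 40.5% | 77.2% |

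**5. Loss against the quit test over a wider grid.** 20-50% smokers, control quitting 5-20%, intervention quitting 15-40%, equal relapse of 0-10%. Points lost at N = 306, median (range):
- exact balance: 21.5 (1.6-27.4)
- blocks of 2: 18.8 (1.3-24.4)
- blocks of 4: 17.4 (1.4-22.5)
- blocks of 6: 16.0 (1.0-21.6)
- no stratification: 13.5 (1.0-19.0)

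With 230 patients (306 x 0.75, for 25% dropout) and blocks of 4, the loss is 15.2 (3.7-21.9).

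**The case against.** The strongest reply is that an omnibus test is being compared with a contrast chosen in the knowledge that only quitting changes. That is fair. When relapse falls as well, the planned test can beat the quit-only test (57.6% against 40.5% in the last table row). The stratified overall test gains about 20 points in that row, but only about -3 to +3 in the block-of-4 rows where quitting alone changes. Two separate tests at 5% each would also produce at least one false positive with probability 1 - 0.95² = 9.75% per visit.

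Some stronger readings are tempting, but the documents do not support them:
- A reader might infer a fixed large loss of power. No smoking, quit or relapse rate is stated, and the loss is only a few points where power is already very high.
- A reader might blame the stratification. The median loss is still 13.5 points without it.
- A reader might call the p-value invalid. A size below 5% does not inflate false positives.
- A reader might say the direction of change would be hidden. The p-value alone does not give it, but the shift table reports all four categories by group and visit.
- A reader might see a damaged efficacy claim. Section 7.B makes this analysis exploratory and bars causal interpretation.

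What remains is that Visit 0 status cannot show a treatment effect, and no reason is given for testing it as part of the outcome.

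**Conclusion.** The point holds as a minor one. The four-category test includes a pre-treatment stratification factor and is somewhat conservative under the planned randomisation, with a size of about 1 to 4% at nominal 5% according to block size. For a pure cessation effect it typically loses about 10 to 25 points of power against a comparison among Visit 0 current smokers. The size and power ranges rest on assumed smoking, quit and relapse rates, the power range on equal relapse in both groups. Most of the loss comes from the 3 df omnibus form and a smaller part from the balanced baseline component. The consequence is confined to an exploratory secondary result.

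**What to change.** In section 7.B.3.5, changes in smoking status:
- Keep the four-row shift table as description, with percentages calculated within each Visit 0 status.
- Replace the four-category test by comparisons within Visit 0 status: quitting among Visit 0 current smokers as the main contrast, and relapse among Visit 0 ex-smokers reported separately, each by chi-square or Fisher's exact test.
- If one overall directional test is wanted, use a Cochran-Mantel-Haenszel test of current smoking at the visit, stratified by Visit 0 status.

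This changes wording only and needs no new data or patients. Three costs should be stated with it. Two tests at 5% raise the chance of at least one false positive to about 10% per visit, with no multiplicity adjustment planned. The quit-only test ignores any benefit on relapse. The stratified overall test gains little if only quitting changes.

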Individual # 4	60-90	
 
- Knowledge assessment
 
- Disease knowledge: importance of nutrition, sleep and physical activity
 
- Behaviour change: smoking cessation; compliance to medication; maintain an active life; integrate healthy habits in everyday life
 
- Self-management skills: methods to increase physical and leisure activities, while adhering to oxygen therapy; keep healthy sleep and nutrition habits
 
	
 
- Handbook “Adopt and maintain a healthy lifestyle”
 
- Module “Long term oxygen therapy”
 
- Brochure “Summary guide”
 
	
 
- Trainer guide “Adopt and maintain a healthy lifestyle”
 
- Flipchart
 

Group	90-120	
 
- Needs assessment
 
- Behaviour change: maintenance of healthy habits and integration of self-management skills for life
 
- Self-management skills: brief review of all self-management techniques; focus on action plan: symptoms monitoring, respiratory self-assessment; managing symptoms worsening
 
	
 
- Handbook “Integrating an action plan into your life”
 
- Written action plan
 
	
 
- Trainer guide “Group session”
 
- Flipchart
 

Phone	30	
 
- Assessment of behaviour change: integrated behaviours, barriers to change and reasons (knowledge, beliefs, etc...)
 
- Self-efficacy reinforcement on various self-management skills
 
		
 
- Standardised educational phone interview
 

The program will be administered to the patient by health professionals (*nurses, physiotherapists, ...*), called for the study purpose “health counsellors”, especially trained to educate COPD patients and to the education program. Duration of each session, content and related materials are listed in Table 1.

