#### 6.A.2.9. Smoking status

Smoking status will be reported by the investigators at Visits 0 to 5, as any changes (*e.g., stopping or re-starting smoking*) may impact the outcome measurements. Results of HbCO measurements performed from the arterial or capillary blood gas sample at Visits 1 and 5 will also be considered.

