### **6.B.2 Laboratory parameters**

Prior to Visits 1 and 5, the following blood samples will be assayed by the laboratory of each investigational centre for each randomised patient:

- Resting arterial or capillary blood gases on room air, *i.e.*, pH, PaO2, PaCO2, HCO3, HbCO and SaO2.
- Venous blood sampling: haemoglobin (*anaemia will be defined as a haemoglobin level below 13 g/dL and polycythemia as a haemoglobin level ≥ 17g/dL for males and ≥ 15g/dL for females*), haematocrit and CRP.

Additional blood samples may be collected at the investigator's discretion, in the patient's interest, in case of technical problems during the initial assays performed and/or clinically significant abnormalities evidenced requiring specific additional checks and follow-up until stabilisation or normalisation.

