## **ARTERIAL OR CAPILLARY BLOOD GASES**

For each arterial blood gas assayed (*i.e.*, pH, PaO2, PaCO2, HCO3, HbCO and SaO2), separately, quantitative descriptive statistics of recorded values will be tabulated by study group (*and globally*) and visit, using the observed case approach.

Moreover, to visualise the evolution of each arterial blood gas assayed, arithmetic means of the recorded values of pH, PaO2, PaCO2, HCO3, HbCO and SaO2, separately and their 95.0% confidence intervals will be represented graphically (*the x-axis being the assessment time-axis and the y-axis being the arithmetic mean-axis*) with both study groups being represented separately on the same graph, using the observed case approach.

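### HbCO is to be considered for smoking status (6.A.2.9), but the group comparison in 7.B.3.5 uses only unblinded reported status; an HbCO-verified comparison should be added at Visit 5

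*Protocol*

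**What the plan says.** **Source of smoking status.** Section 6.A.2.9: "Smoking status will be reported by the investigators at Visits 0 to 5". The next sentence adds: "Results of HbCO measurements performed from the arterial or capillary blood gas sample at Visits 1 and 5 will also be considered".

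**Who has HbCO.** Section 6.B.2 includes HbCO in the resting blood gases taken before Visits 1 and 5, and says that "the following blood samples will be assayed by the laboratory of each investigational centre for each randomised patient".

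**The comparison.** Section 7.B.3.5 tabulates current smokers and ex-smokers, builds a four-category shift table from Visit 0, and says that at each visit "the smoking status evolution since Visit 0 will be compared between both study groups", by Pearson's chi-square or Fisher's exact test. It gives no role to HbCO: no cut-off, reclassification, concordance table or sensitivity analysis.

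**Where HbCO is analysed.** Only in 7.B.3.7, under the blood gases, where a passage beginning "For each arterial blood gas assayed" provides descriptive statistics and plots of means by group and visit.

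**Blinding.** Section 4.B.2: "Neither the patient nor the study personnel of the investigational centre will be blinded as to the study group allocated, after randomisation".

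**Teaching.** Table 1 in 5.A.1.1 lists, for the fourth individual home session of the Intervention group, "smoking cessation; compliance to medication; maintain an active life". Its group and phone sessions reinforce healthy habits and assess behaviour change. Control patients receive the centre's usual education (4.B.3.1, 5.A.2), whose content the protocol does not specify.

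**Status of the result.** Section 7.B makes everything except the primary analysis exploratory and descriptive, tested two-sided at 5% without multiplicity adjustment.

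**The concern.** Two parts of the protocol do not meet. The efficacy section says that an objective measure will inform smoking status. The analysis section then fixes the classification and the test without it. Group means of HbCO among the safety tables cannot show whether a particular reported quitter was still smoking.

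This matters because the reporting is open and the two groups are not followed up in the same way. A patient taught to stop smoking and then contacted repeatedly about behaviour may be more inclined to say that he or she has stopped. The investigator who records the answer knows the allocation. If over-reporting is more common in the Intervention group, a difference in reported quitting can arise without any difference in smoking. For hospital days the protocol guards against subjectivity with a hard endpoint (1.B) and a blinded committee (6.D). Smoking status has no such safeguard in its analysis, although the assay is already planned.

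**Working it through.** The protocol gives no smoking prevalence, quit rate or misreporting rate, and no sample-size figure for this criterion, so there is no stated figure to reproduce. The arm size comes from 7.B.2: 143 evaluable patients per group (153 randomised, since 143 / (1 - 0.0625) = 152.5).

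**Assumed inputs**
- 55 current smokers per arm at Visit 0. They are equal across arms because randomisation takes smoking status into account (3.A, 4.B.2).
- True quit rate q = 10% in both arms, so there is no true effect.
- 5% relapse among the 143 - 55 = 88 ex-smokers per arm.
- Share m of continuing smokers who report having quit: 10%, 20% and 20% in Intervention against 5%, 10% and 5% in Control.

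**Step 1, reported quit rates.** Reported rate = q + (1 - q) × m.
- m = 5%: 0.10 + 0.90 × 0.05 = 14.5%
- m = 10%: 0.10 + 0.90 × 0.10 = 19%
- m = 20%: 0.10 + 0.90 × 0.20 = 28%

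**Step 2, the planned test.** Pearson chi-square, the sum of (O - E)² / E over the 2 × 4 table (ex/ex, current/current, ex/current, current/ex), on 3 degrees of freedom at 5%. I simulated 100,000 trials per scenario and counted significant results with more reported quitters in Intervention.

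| Misreporting, Intervention / Control | Reported quit rates | Planned test favours Intervention |
|---|---|---|
| none | 10% / 10% | 0.8% |
| 10% / 5% | 19% / 14.5% | 3% |
| 20% / 10% | 28% / 19% | 8% |
| 20% / 5% | 28% / 14.5% | 20% |

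The null figure lies below 2.5% because the number of smokers is held equal in both arms. The statistic then varies on only two degrees of freedom but is judged on three: P(chi-square on 2 df > 7.815) = exp(-3.91) = 2.0% two-sided, or about 1% in one direction.

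**Step 3, sensitivity to the assumptions.**
- With 40 to 70 smokers per arm, the last three rows become roughly 2-4%, 6-10% and 14-27%.
- With 153 per arm they hardly change.
- If the number of smokers varies between arms (38% smokers, 143 per arm), the two-sided rejection rates are about 7%, 12% and 27%, against about 4.6% with no misreporting.

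**Step 4, what HbCO can cover.**
- Visits 0, 2, 3 and 4: no HbCO is planned.
- Visit 1: the sample may predate randomisation, since tests from the preceding 3 months are accepted (4.B.3.1, 6.E).
- Visit 5: the sample may fall at any time after Visit 4 (4.B.3.2, 6.E).

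Verification is therefore realistic only at Visit 5.

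**The case against.** **This is SAP detail.** The protocol commits to considering HbCO, and the cut-off and tables can sit in an analysis plan that is not shown. This stands for the cut-off. It does not stand for the comparison itself: 7.B.3.5 already fixes the categories, visits and tests for smoking status, and HbCO is not among them.

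**The consequence is small.** This stands. Smoking status is the last of nine secondary criteria, and 7.B rules out causal interpretation of everything but the primary analysis. Reported smoking status at Visit 1 also enters the exploratory regression as a candidate factor, but the primary Wilcoxon test does not use it.

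**The two groups may be taught alike.** A reader might infer that only Intervention patients are taught to stop smoking. The protocol does not say so: usual centre education may include cessation advice, and the group and phone sessions in Table 1 do not name smoking. What the documents support is that the Intervention teaching and follow-up are specified and repeated, while the Control content is left open. Likewise, the protocol says that investigators report the status. That the source is the patient's own account is a fair inference, not its wording. The report is unblinded either way.

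**HbCO is an imperfect check.** This stands. It reflects recent smoking only, so it cannot confirm the six months of abstinence that define an ex-smoker at Visit 0 (4.B.1.2). A patient who stopped after the Visit 5 sample would look like a smoker, and some samples will be missing. These limits argue against replacing reported status with HbCO. They do not argue against showing the two side by side.

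**Conclusion.** The point holds as a mismatch within the protocol and a cheap improvement. Section 6.A.2.9 says HbCO will be considered, 6.B.2 has it assayed in every randomised patient, and 7.B.3.5 compares the groups without it. As written, a favourable smoking result could not be separated from over-reporting.

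On the assumed inputs, differential misreporting raises the chance of a result favouring Intervention from 0.8% to about 3%, 8% or 20%. In the mildest case that is close to the nominal 2.5%. The direction is clear, but the size depends wholly on assumed prevalence, quitting, relapse and misreporting.

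A reader might reach 9%, 20% and 42% by testing quitting among the 55 smokers per arm alone. Those figures are correct for that test, but the protocol plans a four-category test in all patients, which dilutes the difference. A reader might also conclude that HbCO-verified status should become the main analysis. The documents do not support that: there is no HbCO at Visit 0, where the shift table starts, and the Visit 5 sample need not coincide with the reported status.

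**What to change.** In 7.B.3.5, add an HbCO-verified comparison at Visit 5, reported beside the reported-status comparison:

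1. Among patients who were current smokers at Visit 0, count a reported quitter as verified only if the Visit 5 HbCO is below a cut-off fixed before any group comparison.
2. Tabulate reported status against HbCO by group for all patients with a Visit 5 sample.
3. State the interval between sample and visit.
4. Report missing HbCO by group. As a sensitivity analysis, count missing HbCO as not verified, for reported quitters only.
5. Do not reclassify long-term ex-smokers because HbCO is missing; that would create apparent relapses.
6. Keep reported status at the other visits.

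**Cost.** One paragraph in the protocol and a cut-off in the SAP, with no new assay. The e-CRF must hold the Visit 5 sample date; the protocol lists dates expressly for the Run-In samples (4.B.3.1) but not for those at Visit 5. The downside is that HbCO shows recent smoking only, will be missing for some patients, and may not match the reported status in time.
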